9.2.1 Autoimmune disorders

For this category, the primary events are Systemic Lupus Erythematosus and Rheumatoid Arthritis.

The diagnosis has to be supported with medical history and physical findings, serologic evidence and other evidence from biopsy, laboratory results, imaging results, or other specialized testing, where appropriate, and the exclusion of other disorders which might cause a similar pattern of findings.

9.2.2 Demyelinating disorders

For this category, the primary event is Multiple Sclerosis. Guillain-Barre syndrome and chronic inflammatory demyelinating polyneuropathy will be analyzed as autoimmune disorders.

Medical history and physical findings, laboratory results, imaging results (eg, MRI) and any other specialized test (EEG, EMG, CSF analysis) results have to be considered in determining the final diagnosis.

9.2.3 Serious and Opportunistic Infections

Serious infections are defined as all infections meeting the definition of an SAE, and/or an infection requiring parenteral administration of antibiotics.

For the opportunistic infection category, the primary events are tuberculosis and pneumonia. The definitive diagnosis of pneumonia and tuberculosis may be confirmed by obtaining sputum smears or relevant biopsies and verifying by cultures. Infections not usually seen in immunocompetent patients or infections that have an accelerated pathogenesis or a more severe outcome in a given setting will also be considered opportunistic infections.

9.2.4 Lymphoma and Other Malignancies

For this category, the primary events are lymphoma, including hepatosplenic T cell lymphoma and non-Hodgkin lymphoma, and solid malignant tumors.

Diagnosis has to be confirmed by tissue biopsy for histopathology (sources of tissue samples for review may include those obtained from an excisional biopsy -a tissue sample from the affected nodes or organ, a needle aspiration, or a bone marrow biopsy. Pathohistological results have to correlate clinically with imaging results and/or any other pertinent information prior to determining the final diagnosis.

9.2.5 Hypersensitivity Reaction

Primary endpoints for hypersensitivity reaction are events meeting the criteria of an anaphylactic reaction and acute hypersensitivity reaction occurring within 2 hours of drug administration. As described in the case definition below, anaphylactic events include all terms listed in Category A, which consists of the narrow terms Type I hypersensitivity, anaphylactic shock and anaphylactoid reaction. In addition, combinations of the AE terms listed in Categories B, C and D will also be defined as anaphylactic events.

Category A: anaphylactic reaction, Type I hypersensitivity, anaphylactic shock, anaphylactoid reaction

Category B: dyspnoea, chest discomfort, cough, swollen tongue, oedema mouth, throat tightness, wheezing, laryngeal oedema, respiratory distress, sensation of foreign body, asthma, sneezing

Category C: swelling face, urticaria, pruritus, rash, eye swelling, pruritus generalized, rash, generalized, flushing, erythema, swelling, eye pruritus, lip swelling, rash pruritic, rash, erythematous, eyelid oedema, ocular hyperaemia, injection site urticaria, angioedema

Category D: hypotension, blood pressure decreased

To meet the definition of an anaphylactic event, a case has to meet one of the following criteria:

4. A narrow term or a term from Category A;
5. A term from Category B (Upper Airway/Respiratory) AND a term from Category C (Angioedema/Urticaria/Pruritus/Flush);
6. A term from Category D (Cardiovascular/Hypotension) AND either a term from Category B (Upper Airway/Respiratory) or a term from Category C (Angioedema/Urticaria/Pruritus/Flush)

9.2.6 Congestive heart failure

Congestive heart failure (CHF) is the primary endpoint for cardiac events of interest. CHF will be defined by Framingham criteria. The diagnostic criteria include physical findings of low cardiac output or increased cardiac workload and radiographic evidence (chest X-ray, ECG, Echocardiogram, CT, MRI, angiogram) and laboratory findings, ECG and imaging results and any other specialized test results have to be considered for final diagnosis. CHF present at baseline and worsening during the study (worsening of New York Heart Association (NYHA) functional classification) will be captured, as well as new onset CHF.

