3 REGISTRY OBJECTIVE

The objective of this registry is to measure the safety outcomes among Cimzia patients compared to those that occur while on a different CD treatment regimen.

All SAEs and AEs of interest will be collected and summarized (see Section 5). The AEs of interest are: selected autoimmune disorders and demyelinating disorders, serious infections including opportunistic infections, hypersensitivity reactions, lymphoma and other malignancies. In addition, UCB plans to evaluate aplastic anemia and serious cardiac events (specifically, CHF). All these events represent serious risks known to the class of tumor necrosis factor (TNF) blocking agents. During the development program for CD and rheumatoid arthritis consisting of over 6,000 subjects, reported events were consistent with the class.

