4.8.1 Enrollment Visit

For each patient enrolled in this registry, the Investigator will document the following information into the corresponding eCRFs within the registry study EDC system:

- Demographic information such as gender, age, race, ethnicity, household income, occupation and smoking status
- Crohn's disease history, including length of time since initial presentation of symptoms, date of diagnosis, all past treatment and surgeries for CD (with special focus on anti-TNF α and other biologics), and reason for switch to Cimzia or other medications since diagnosis and within the past 3 months
- Investigator's assessment of CD severity
- Investigator's completion of the Harvey-Bradshaw Index (HBI) – See Section 12.1 APPENDIX A. This may also be completed by qualified site personnel as designated by the Investigator
- Patient's assessment of CD severity
- Patient's completion of the modified HBI. The modified HBI does not include the abdominal mass question contained in the full HBI

- Other medical history including current medical status, concomitant medications, and planned treatment period (if known) with special focus on previous occurrence of each AE of interest and related risk factors (eg, history of serious infections, conditions that might place a patient at higher risk of serious infection)

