5.2.6 Congestive heart failure

Congestive heart failure (CHF) is the primary endpoint for cardiac events of interest. CHF will be defined by Framingham criteria. The diagnostic criteria include physical findings of low cardiac output or increased cardiac workload and radiographic evidence (chest X-ray,

ECG, Echocardiogram, CT, MRI, angiogram) and laboratory findings, ECG and imaging results and any other specialized test results have to be considered for final diagnosis. CHF present at baseline and worsening during the study (worsening of New York Heart Association (NYHA) functional classification) will be captured, as well as new onset CHF.

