8.1.4 Incidence and event rate calculation

In general, for each, the cumulative incidence, incidence rate and corresponding 95% confidence interval will be presented. For the incidence rate, the numerator will be the total number of patients experiencing the AE of interest for the first time in the study (if a patient switches treatment and has an AE of interest it will be considered a recurrence if the AE occurred while on a previous treatment). The denominator will be in 100 patient-years. That is, the denominator will be the total summation of individual patient-years at risk up the first occurrence of the AE of interest for subjects with that AE, and the total patient-years at risk for those subjects not experiencing that AE, divided by 100. Two-sided 95% confidence intervals for the incidence rates are calculated [using the GAMINV function in SAS] to determine the upper and lower limits for the number of events for each AE of interest, which is assumed to follow a Poisson distribution, divided by the total patient-years of exposure multiplied by 100. [Note that the method to be used follows a SAS implementation using the GAMINV function and is described in detail on bottom, right hand side of p. 2 and the code in the box on the left hand side of p. 3 in the SUGI paper <http://www2.sas.com/proceedings/sugi26/p241-26.pdf>].

A Poisson AE of interest regression analysis, accounting for within-patient correlations, implemented with the GENMOD procedure in SAS, is used to test for the differences in incidence rates between actual treatment cohorts at the two-sided $\alpha=0.05$ level. Potential code for these models is:

```
PROC GENMOD data = XXXXX;  
CLASS COHORT;  
MODEL AEOFINT = COHORT / D = POISSON OFFSET = LPRSNYRS;  
RUN;
```

Where AEOFINT is the number of events for a particular AE of interest, LPRSNYRS is the log of the total number of patient-years, and COHORT represents the actual treatment cohorts. Type III analysis will be used to get the cohort effects conditional on all covariates listed above in Section 4.1.

For event rates, the numerator will be the number of AEs of interest, including repeat occurrences in individual subjects. The denominator will be the total exposure in 100 patient-years, without censoring the exposure to the first event. That is, the total summation of individual patient-years divided by 100. No confidence intervals will be computed for event rates.

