8.2.2 Adverse Events

Any event reported by the investigator or found in the drug safety database excerpt is considered an adverse event. Investigator and drug safety AEs have been reconciled by the study physician to avoid over reporting.

When an AE is considered serious in either source, it is treated as serious in the analysis and the related coding data is used.

Events reported in the patient survey are not considered confirmed AEs and are excluded from the analysis.

AE tabulations will be done using malignancy rules (for malignancies) separately using acute event rules (all AEs) unless otherwise specified.

A summary of study-emergent AEs, including the number of events reported, the number and percentage of patients reporting at least one AE, the number and percentage of patients reporting at least one AE of Interest, the number and percentage of patients with at least one serious AE (SAE), and the number and percentage of deaths will be presented. In addition, the number and percentage of patients reporting at least one study-emergent treatment-related AE, the number and percentage of patients reporting at least one study-emergent treatment-related AE of Interest, and the number and percentage of patients with at least one study-emergent treatment-related SAE will also be reported. AE summaries will be produced on the enrolled cohort as well as the malignancy/acute event rules.

Study-emergent AEs are those which first occur or increase in relationship to treatment after the first dose of any CD drug following enrollment.

A breakdown of the number and percentage of patients reporting each AE as well as the number of AEs, categorized by SOC, HLT, and PT coded according to MedDRA, will be presented. Note that patients are only counted once within each SOC, HLT, or PT. Uncoded AEs will be summarized in unknown SOC, HLT and PT. This will be produced for the enrolled cohort as well as both the malignancy and acute event rules.

A further tabulation of these data, broken down by relationship to treatment, will be presented. Patients with multiple events within a particular body system or preferred term will be counted under the category of their most drug-related event within that SOC, HLT or PT. Relationship to treatment is categorized as related or not related as collected on the eCRF.

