8.2.3 Adverse Events of Interest

The AEs of interest and the approach for summarizing them is briefly described below. Further information is provided in the guidance document (AEs of Interest – Cimzia Program 2018-01-05).

- Serious infections, including opportunistic infections. Serious infections will be summarized using the Serious TEAE table. In addition, opportunistic infections (including tuberculosis) will be presented in a table using UCB-defined search criteria.
- Malignancies, including lymphoma. These will be presented in 2 tables using the Standardized MedDRA Query (SMQ) criteria “Malignant or unspecified tumours” and “Malignant tumours” respectively.
- Serious cardiovascular events (also called major adverse cardiac events or MACE). These will be presented in a table including all serious TEAEs with the SMQs of “Haemorrhagic central nervous system vascular conditions”, “Conditions associated with central nervous system haemorrhages and cerebrovascular accidents”, and “Ischaemic central nervous system vascular conditions” with the exception of events coding to a PT of “Transient ischaemic attack”, including all serious TEAEs with the HLT of “Ischaemic coronary artery disorders” except events coding to PTs of “Chest Pain” or “Chest discomfort” and including all serious TEAEs with HLTs of “Heart Failures NEC”, “Left Ventricular Failures”, or “Right Ventricular Failures” and which also code to the SOC of “Cardiac Disorders”.
- Congestive heart failure. These will be manually identified by the study physician from the TEAE table.
- Demyelinating-like disorders will be presented in table which is based on the SMQ = “Demyelination”. The SMQ search should include all TEAEs which code to a PT included in Scope=Narrow group within the SMQ. TEAEs which code to a PT included in the Scope=Broad group within the SMQ should be excluded from the search.
- Aplastic anemia, pancytopenia, thrombocytopenia, neutropenia, and leucopenia. These will be presented in a table using the criteria SMQ = “Haematopoietic cytopenias” in the subset of Serious TEAEs.
- Serious bleeding events. These will be presented in a table using the criteria SMQ = “Haemorrhage terms (excl laboratory terms)” in the subset of Serious TEAEs.
- Lupus and lupus-like illness. These will be manually identified by the study physician from the TEAE table.

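### The plan does not separate new-onset CHF from worsening of existing CHF, and prior-CHF patients stay in the risk set, so the CHF ratio can reflect baseline case mix

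*Protocol*

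**What the plan says.** **Endpoint.** Protocol 5.2.6 makes CHF the primary endpoint among cardiac events of interest and brings two kinds of event under it. One is deterioration of existing disease: "CHF present at baseline and worsening during the study (worsening of New York Heart Association (NYHA) functional classification) will be captured". The other is added at the end of the same sentence: "worsening of New York Heart Association (NYHA) functional classification) will be captured, as well as new onset CHF".

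**Case finding.** SAP 8.2.3: "Congestive heart failure. These will be manually identified by the study physician from the TEAE table". SAP Table 8.1 lists CHF once, as an acute event. Neither place divides onset from worsening.

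**What is eligible for selection.** The nearest definition in the SAP is in 8.2.2: "Study-emergent AEs are those which first occur or increase in relationship to treatment after the first dose of any CD drug following enrollment". A change in severity or NYHA class is not mentioned.

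**Incidence.** SAP 8.1.4: "the numerator will be the total number of patients experiencing the AE of interest for the first time in the study". The denominator is time to that event, or all time at risk for patients without one. The acute person-time rules (SAP 3.2.1.2) and the Full Analysis Set (SAP 3.5.2) exclude no one for a history of the event.

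**Adjustment.** The covariates named in SAP 4.1 and 8.1.2 include no CHF, cardiac history or other comorbidity.

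**Available data.** At enrollment, Protocol 4.8.1 collects medical history with "special focus on previous occurrence of each AE of interest and related risk factors". SAP 6.2 tabulates conditions of interest by cohort but makes no further use of them.

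**The concern.** Whether a drug causes heart failure and whether it worsens existing heart failure are different questions with different populations at risk. The first concerns patients free of CHF at baseline; the second concerns only those who have it. One row, with everyone in the denominator, answers neither cleanly.

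The rate of worsening in patients with CHF may well be many times the rate of new onset in patients without it. If so, a small group with prior CHF can supply a large share of the events. The ratio between exposure groups then partly measures how many such patients each group contains. Protocol 6.4.1.3 accepts that treatment choice in this registry is not random, so equal prevalence cannot be taken for granted.

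The silence on whether worsening counts is a defect under either reading. If it counts, decompensation of known CHF is reported as incidence. If it does not, an outcome that Protocol 5.2.6 says is captured has no analysis, and patients who cannot have new onset remain in a new-onset denominator. The choice falls to manual selection with no written rule.

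**Working it through.** The documents give no CHF rate, no baseline CHF prevalence and no CHF power figure, so there is no stated figure to reproduce. The check asks how large the distortion could be when the drug has no effect.

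**Inputs from the documents (Protocol 6.3)**
- Dropout 8% a year, so λ = −ln(0.92) = 0.0834 per year.
- Follow-up T = 8 years.
- Enrolled: 1371 Cimzia, 1674 comparator.

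**Assumed inputs**
- New onset o = 0.2 per 100 patient-years in patients without prior CHF.
- Worsening w = 5, 10 or 20 per 100 patient-years in patients with prior CHF.
- Baseline CHF prevalence p in each group, as shown in the last table.
- Constant hazards, no switching, worsening counted.

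**Formulas (time stops at the first event, as in SAP 8.1.4)**
- Events per patient at hazard h: e(h) = h/(h+λ) × [1 − exp(−(h+λ)T)]
- Person-years per patient: y(h) = [1 − exp(−(h+λ)T)]/(h+λ)
- Group rate = [p·e(w) + (1−p)·e(o)] / [p·y(w) + (1−p)·y(o)]

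| Hazard (per 100 p-y) | e | y |
|---|---|---|
| 0.2 | 0.01159 | 5.797 |
| 5 | 0.2459 | 4.918 |
| 10 | 0.4196 | 4.196 |
| 20 | 0.6326 | 3.163 |

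**One case in full: 1% v 2%, w = 5**
- Cimzia: (0.01 × 0.2459 + 0.99 × 0.01159) / (0.01 × 4.918 + 0.99 × 5.797) = 0.01394/5.788 = 0.241 per 100 p-y.
- Comparator: (0.02 × 0.2459 + 0.98 × 0.01159) / (0.02 × 4.918 + 0.98 × 5.797) = 0.01628/5.779 = 0.282 per 100 p-y.
- Ratio = 0.241/0.282 = 0.85.

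**Ratio with no drug effect**

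| Prevalence, Cimzia v comparator | w = 5 | w = 10 | w = 20 |
|---|---|---|---|
| 1% v 2% | 0.85 | 0.79 | 0.74 |
| 0.5% v 1% | 0.92 | 0.87 | 0.82 |
| 2% v 1% | 1.17 | 1.26 | 1.36 |
| 1% v 1% | 1.00 | 1.00 | 1.00 |

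At 2% prevalence, worsening makes up 30% (0.02 × 0.2459/0.01628) to 53% (0.02 × 0.6326/0.02401) of the events labelled incident CHF.

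**Sensitivity to the time rule.** Without stopping time at the first event, the group rate is (1−p)·o + p·w. The 1% v 2% ratios are then 0.248/0.296 = 0.84, 0.298/0.396 = 0.75 and 0.398/0.596 = 0.67. The first-event figures follow the plan's rule and are somewhat nearer to 1.

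**If worsening is not counted.** Only the denominator is affected: 0.99/0.98 = 1.01 at 1% v 2%.

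**After separation.** Among patients without prior CHF, both groups have rate o and the ratio is 1.00 in every row.

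**Precision.** In the worked case, expected events are 1371 × 0.01394 = 19.1 and 1674 × 0.01628 = 27.3. The standard error of the log ratio is √(1/19.1 + 1/27.3) = 0.298. A 95% interval around 0.85 runs from about 0.48 to 1.53.

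**The case against.** The other side has four good arguments.

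**Pooling is not stated.** Protocol 5.2.6 speaks of capture and names the two events separately, and the study-emergent definition in SAP 8.2.2 does not mention severity. A reader might infer that every decompensation will be counted as incident CHF; the documents do not say so. This stands, and it is why the point is conditional. It does not remove the need for a rule.

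**The direction is unknown.** A reader might infer that CHF patients are steered away from Cimzia, so that the ratio flatters it. The protocol does say of the events of interest, CHF among them, "All these events represent serious risks known to the class of tumor necrosis factor (TNF) blocking agents". But that is a class risk, and the comparator includes other anti-TNF drugs (SAP 3.6). Protocol 6.4.1.3 does not list CHF among the drivers of treatment choice. The documents do not support a bias in Cimzia's favor.

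**This is confounding by prior CHF, and adjustment could remove it.** That is correct for the ratio. SAP 8.1.2 calls for all collected potential confounders and leaves its list open, so prior CHF may be included, but nothing commits the analysis to it. Adjustment would also leave each group's rate a mixture, and the adjusted ratio would still blend onset with worsening.

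**The stakes are limited.** The primary outcome is malignancy, no formal hypothesis is tested, and the power statement does not cover CHF. The illustrative shift lies well inside the sampling error shown above. This stands and sets the priority. Worsening of CHF is also a legitimate safety outcome, which argues for its own row.

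**Conclusion.** The point holds in a conditional form. As written, the plan yields a CHF incidence ratio whose numerator is not fully specified and whose risk set includes patients with prior CHF. The ratio departs from the drug effect only if worsening is counted, baseline CHF prevalence differs between exposure groups, worsening and onset rates differ, and prior CHF is left unadjusted. Under the assumed inputs the no-effect ratio runs from 0.74 to 1.36 according to which group holds more prior CHF. The documents fix neither size nor direction. Keeping prior-CHF patients in the denominator alone matters by about 1%.

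A reader might extend the argument to rheumatoid arthritis, lupus and multiple sclerosis, because the same first-in-study rule applies to them. The documents do not support that: only the CHF section provides for capturing worsening of disease present at baseline.

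This is a worthwhile change of modest priority.

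**What to change.** - In SAP 8.2.3, state whether NYHA worsening of baseline CHF counts as a CHF event, and have the study physician classify each selected case as new onset or worsening.
- In SAP 8.1.4, compute CHF incidence (rate, confidence interval, hazard ratio) among patients with no CHF in the baseline history.
- Add a row to Table 8.1 for NYHA worsening among patients with prior CHF. The combined row may stay as a supplement.
- If the combined ratio is kept, name prior CHF as a covariate for it.

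The cost is a filter on history already collected, one classification per CHF case and one more row. The new-onset row loses a little person-time and some events, and the worsening row will be sparse and may support only counts and a rate.

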9.2.7 Aplastic anemia

Aplastic anemia is a primary endpoint. Diagnosis must be confirmed by complete blood count (CBC) with peripheral smear, and bone marrow biopsy. Findings of pancytopenia (neutropenia, thrombocytopenia, and anemia), a reduction in the absolute number of reticulocytes, and a hypocellular bone marrow could be used to confirm the diagnosis.

9.2.8 Serious bleeding events

For this category, bleeding events meeting the criteria of an SAE are primary endpoints.

9.2.9 Serious skin reactions

For this category, primary endpoints are Erythema multiforme, Stevens Johnson's syndrome, and Toxic epidermal necrolysis.

Change #20

Deletion of former Section 9.4 through Section 9.6

9.4 Case Definition:

Cimzia Case:

Cases will be attributable to Cimzia identified by two methods. The first method will assume a case will be attributable to Cimzia after the first dose of the medication regardless of medication discontinuation and time to onset of the event. The second method will be a series of sensitivity analyses and stratifications to evaluate different clinically driven definition of cases attributable to drug. Specifics on data handling guidelines for managing missing or partial data will be documented in the Statistical Analysis Plan (SAP).

Control Case:

Cases will be attributable to non-Cimzia medications identified by two methods. The first method will assume a case will be attributable to the non-Cimzia medication after the first dose of the medication regardless of medication discontinuation and time to onset of the event. The second method will be a series of sensitivity analyses and stratifications to evaluate different clinically driven definition of cases attributable to drug. Specifics on data handling guidelines for managing missing or partial data will be documented in the SAP.

9.5 Exposure Definition:

Cimzia Exposure:

Cimzia exposure will be calculated by two methods. The first method will assume exposure from day one of the first dose of Cimzia medication after enrollment regardless of medication discontinuation through the date of the last follow-up evaluation. The second method will be a series of sensitivity analyses and stratifications to evaluate the different clinically driven definitions of exposure to drug. Specifics to these definitions will be outlined in the SAP.

Control Exposure:

Non-Cimzia medication exposure will be calculated by two methods. The first method will assume exposure from day one of the first dose of the non-Cimzia medication after enrollment regardless of medication discontinuation through the date of the last follow-up evaluation. The second method will be a series of sensitivity analyses and stratifications to evaluate the different clinically driven definitions of exposure to drug. Specifics to these definitions will be outlined in the SAP.

